### **Statistical Analysis**

If a continuous variable follows a normal distribution, it is represented by the mean and standard deviation; if it does not follow a normal distribution, it is represented by the median and interquartile range. The treatment effectiveness is presented as the improvement percentage based on the pre- and post-treatment sleep habit questionnaire, depression questionnaire, anxiety questionnaire, stress questionnaire, digestive symptom questionnaire, and irritable bowel syndrome questionnaire. The efficacy of diaphragmatic breathing was assessed using a Chi-squared test to compare percentages. A P-value less than 0.05 was considered statistically significant. The statistical analysis software used is SPSS 19 (SPSS, Inc, Chicago, IL, USA).

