### F. Project Abstract

Please provide a brief overview of the key points of this project within 500 words and customize keywords based on the nature of the project.

Patients with disorders of gut-brain interaction (DGBI) often present gastrointestinal symptoms that do not show noticeable irregularities in standard examinations. However, due to unclear causes and a high prevalence rate, this condition often exerts a profound impact on the physical and mental health of patients. The scope of DGBI encompasses conditions such as laryngopharyngeal reflux, functional dyspepsia, and irritable bowel syndrome. Previous research has confirmed that in patients with DGBI, their autonomic nervous system exhibits an imbalance, characterized by decreased parasympathetic activity and dominant sympathetic activity. Diaphragmatic breathing helps reduce the respiratory rate and can stimulate parasympathetic activity while suppressing sympathetic activity. Hence, it is now officially recommended as an effective adjunct therapy for relieving symptoms of gastroesophageal reflux. Accordingly, this study plans to implement a randomized controlled trial, introducing diaphragmatic breathing to patients with DGBI who exhibit normal results in objective examinations. This work allows evaluate changes in their psychophysical symptoms before and after treatment, as well as alterations in the autonomic nervous system.

**Key words**: disorders of gut-brain interaction, psychophysical symptoms, diaphragmatic breathing, autonomic nervous system

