### Hypothesis 2 : Diaphragmatic breathing can improve symptoms in patients with DGBI.

Hypothesis 2-1 : Introducing diaphragmatic breathing can improve symptoms in patients with Laryngopharyngeal Reflux Disease (LPR).

Hypothesis 2-2 : Introducing diaphragmatic breathing can improve symptoms in patients with Functional Dyspepsia (FD).

Hypothesis 2-3: Introducing diaphragmatic breathing can improve symptoms in patients with Irritable Bowel Syndrome (IBS).

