### **Research Methods**

### Participant

The trial is expected to last for 1 year, with a research period ending on December 31, 2024. It aims to recruit 600 participants, including 150 healthy volunteers to be solicited through advertisements. Additionally, 150 participants with Laryngopharyngeal Reflux (LPR) will be recruited from the Gastroenterology Outpatient Department, along with 150 participants with Functional Dyspepsia (FD) and 150 participants with Irritable Bowel Syndrome (IBS). The inclusion and exclusion criteria for participants are as follows :

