### **Research Process Diagram**

### **Finish experiment**

### **Research Steps**

The subjects who meet the inclusion criteria of this study will undergo an initial assessment of heart rate variability and psychosomatic symptoms after enrollment. Subsequently, a two-week

experiment will be conducted, during which the subjects will receive one session of diaphragmatic breathing training by the researchers. After the guided training, the subjects will undergo another assessment of heart rate variability. In the first week, participants will engage in self-practice of the instructed content twice daily, each session lasting 5 minutes, and will record a weekly diaphragmatic breathing diary.

After the first week, subjects will undergo another assessment of heart rate variability and psychosomatic symptoms. In the second week, participants will continue daily self-practice with two sessions of instructed content, each lasting 5 minutes, and will maintain a diaphragmatic breathing diary. Following the second week, subjects will undergo a final assessment of heart rate variability and psychosomatic symptoms, completing the experiment.

Researchers recommend spending approximately 15 minutes on diaphragmatic breathing training, 15 minutes on measuring heart rate variability, and approximately 20 minutes for questionnaire completion. The measurement of heart rate variability utilizes a non-invasive device called "LEADTEK" portable electrocardiogram recorder (Ministry of Health and Welfare Medical Device Manufacturing License No. 006972). If participants have any questions or concerns during the abdominal breathing training process, they are encouraged to contact the researchers.

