- Taiwanese Depression Scale (TDQ) 42 includes three parts: emotion, cognition and body, with a total of 18 questions, and the scale is scored on a four-point scale. Each question is scored on a scale from 0 to 3, and the total score ranges from 0 to 54 points. Those with a score greater than 18 indicate depressive symptoms.
- State-Trait Anxiety. Inventory (STAI) 43 includes two subscales, the Situational and Trait Anxiety Scale, with a minimum score of 20 and a maximum score of 80, with higher scores representing anxiety symptoms.
- The Perceived Stress Scale (PSS-10) 44 is to evaluate the degree of stress in personal life situations, and the higher the score, the greater the stress.
- Esophageal Hypervigilance and Anxiety Scale (EHAS) 41 Esophageal hypervigilance and anxiety can cause symptoms in patients with chronic esophageal diseases, including gastroesophageal reflux, esophageal atlasia and functional esophageal diseases. The questionnaire contains 15 items and can be divided into two main categories . Section: Symptoms of Esophageal Hypervigilance and Symptoms of Esophageal Anxiety. This questionnaire can not only assess the sensory system symptoms of any esophagus-related diseases, but also assist in the diagnosis of functional esophageal diseases.
- Laryngeal Hypervigilance and Anxiety Scale (LHAS) 41 Throat hypervigilance and anxiety can trigger symptoms in patients with chronic esophageal disease. The questionnaire contains 15 items and can be divided into two main parts: throat hypervigilance symptoms and throat anxiety symptoms. This questionnaire can not only assess the sensory system symptoms of any esophagus-related diseases, but also assist in the diagnosis of functional esophageal diseases.
- Visceral Sensitivity Index (VSI) 45 measures anxiety specific to the gastrointestinal tract. It includes 15 items, with a minimum score of 0 and a maximum of 5 points for each item, and a minimum score of 0 and a maximum score of 75 points for the total score.

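### The one efficacy test named, a chi-squared test on an undefined improvement percentage, makes poor use of mostly numeric questionnaire scores or, on other readings, does not fit the data

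*Protocol*

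**What the plan says.** The Statistical Analysis section of the protocol (under H) sets the efficacy measure as follows: "The treatment effectiveness is presented as the improvement percentage based on the pre- and post-treatment sleep habit questionnaire, depression questionnaire, anxiety questionnaire, stress questionnaire", and then lists the digestive symptom and irritable bowel questionnaires. The test follows: "The efficacy of diaphragmatic breathing was assessed using a Chi-squared test to compare percentages". No other test is named. Means with SDs, and medians with interquartile ranges, appear in that section only as descriptive summaries.

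The Questionnaire Evaluation Tool section gives numeric totals for most instruments: functional dyspepsia (FD) 0-52, PSQI 0-21, STAI 20-80 and VSI 0-75. For the depression scale, "the total score ranges from 0 to 54 points". The irritable bowel syndrome (IBS) instrument is the exception. It is described only through Rome IV diagnostic criteria, with onset at least six months ago and pain over the past three months.

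Research Steps places symptom assessments at entry, after week 1 ("After the first week, subjects will undergo another assessment of heart rate variability and psychosomatic symptoms") and after week 2. Hypotheses 2-1 to 2-3 concern laryngopharyngeal reflux (LPR), FD and IBS separately, and the Participant section plans 150 patients for each. On design, the Project Abstract states that "this study plans to implement a randomized controlled trial".

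**The concern.** A chi-squared test works on counts. To use it on a questionnaire total, each person must first be classified, presumably as improved or not. That step treats a one-point gain and a ten-point gain alike, or drops one of them, depending on the cut. It also makes no further use of the baseline score.

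At stake are the three disease-specific hypotheses. Each rests on 150 patients, so a loss of efficiency that would hardly matter in 450 can decide whether a moderate effect is seen. The scores needed for a stronger analysis are already being collected.

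The protocol also does not say which percentages are compared, and the other possible readings fit the test less well than this one.

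**Working it through.** The protocol states no effect size, arm size, responder rate or power, so there is no figure of its own to reproduce. What follows is illustrative.

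**Inputs.** From the protocol: 150 patients per disease, 450 patients in all, and a significance level of 0.05. Assumed: a two-sided test, 1:1 allocation (75 v 75 per disease, 225 v 225 pooled), no dropout, an effect *d* of 0.3-0.5 SD of the change score, 20-50% of controls improved, and normal change scores unless stated.

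**Reading 1: share improved, compared between randomized arms.** If a share p_c of controls improves, the treated share is p_t = 1 - Φ(Φ⁻¹(1 - p_c) - d). At d = 0.5, p_c = 0.50 gives p_t = 0.69 and p_c = 0.20 gives p_t = 0.37. Power of the uncorrected Pearson test comes from exact enumeration of both binomials. Power of the t-test on the change score comes from the noncentral t with noncentrality d√(n/2).

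| Per arm | d | Chi-squared at p_c = 50 / 40 / 30 / 20% | t-test |
|---|---|---|---|
| 75 | 0.5 | 68.7 / 69.5 / 68.3 / 62.1% | 86.0% |
| 75 | 0.4 | 50.9 / 51.1 / 48.8 / 43.5% | 68.2% |
| 75 | 0.3 | 32.6 / 32.6 / 29.8 / 26.5% | 44.6% |
| 225 | 0.5 | 98.6 / 98.9 / 98.6 / 97.7% | 100% |
| 225 | 0.4 | 91.9 / 92.5 / 91.1 / 88.0% | 98.9% |
| 225 | 0.3 | 71.8 / 72.3 / 69.6 / 64.2% | 88.8% |

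Under the null with 75 v 75, the chi-squared test rejects 5.5, 5.5, 4.9 and 5.1% of the time, so it holds its level.

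Sample size for 80% power at d = 0.5:
- Chi-squared with p_c = 0.50, so mean share 0.596: n = [1.96√(2 × 0.596 × 0.404) + 0.842√(0.250 + 0.213)]² / 0.191² ≈ 102 per arm. Over the four cuts the range is about 100-114.
- t-test: 2(1.96 + 0.842)² / 0.5² ≈ 63, or 64 with the t correction.
- ANCOVA on baseline has (1 + ρ)/2 times the variance of the change-score comparison. Thus 64 × 0.65 ≈ 42 per arm at ρ = 0.3 and 64 × 0.90 ≈ 58 at ρ = 0.8. Simulated ANCOVA power with 75 v 75 (20,000 replicates) is 96.6, 93.6 and 89.2% at ρ = 0.3, 0.5 and 0.8.

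**Sensitivity to shape.** With t(5)-distributed changes, 75 v 75 and 0.5 SD, chi-squared power is 76-85% over the same cuts, against about 86% for the t-test. A rank test on the scores reaches 92%. With t(4) changes, chi-squared reaches 82-90% and the t-test about 87%, so the gap to the t-test closes or reverses.

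**Reading 2: shares beyond a cut, before and after, in the same people.** The two shares are correlated, but the ordinary chi-squared test treats them as independent. With a median cut, the correlation of the yes/no outcomes is φ = (2/π)arcsin ρ, and the actual type I error is about 2[1 - Φ(1.96/√(1 - φ))]. This gives 2.9, 1.6 and 0.2% at ρ = 0.3, 0.5 and 0.8. Simulation at n = 150 (40,000 replicates) gives 3.4, 2.0 and 0.3%. For a shift of 0.25 SD of the raw score, simulated power is:

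| ρ | Chi-squared | McNemar | Paired t |
|---|---|---|---|
| 0.3 | 41% | 43% | 73% |
| 0.5 | 40% | 50% | 86% |
| 0.8 | 38% | 69% | 99.8% |

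The first gap in each row is the cost of ignoring pairing; the second is the cost of the yes/no cut.

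**Reading 3: percent change per person.** This is a measurement and not a count, so a chi-squared test does not apply.

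**The case against.** The yes/no classification is inferred. The section gives no responder cut and never says that participants are classified. The reading between arms rests on the abstract's description of the design, while the analysis text speaks of pre- and post-treatment values. A further reading is open, in which improvement percentages are compared across the recruited groups; those groups differ by diagnosis and are not randomized, so that comparison would not test efficacy. All this stands, and it is why the power figures are illustrations.

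A responder percentage is a legitimate and readable endpoint, and on the first reading the test is valid. That also stands. It supports keeping the percentage as a secondary summary, but not as the only basis for judging efficacy.

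The size of the loss depends on normal change scores, and the protocol itself allows for non-normal data. This stands in part: heavy tails shrink or remove the gap to the t-test, but a rank test on the same scores still does better.

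A responder definition and model details may properly sit in a statistical analysis plan. Agreed, and their absence is not the point. The point is the test that the protocol does name, which a later plan would inherit.

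Hypothesis 2-3 has less to lose, because the IBS instrument has no described numeric score. True for that instrument, although general numeric scales are also collected in those patients.

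**Conclusion.** The point holds as a should-fix. The protocol fixes a chi-squared test on an undefined percentage as its only efficacy test. Each plausible reading is either inefficient (shares between arms), conservative because pairing is ignored (shares within persons), or outside what the test can handle (percent change).

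On the first reading, with 75 v 75, normal changes and 20-50% of controls improved, the loss against a t-test is about 16-24 percentage points of power at 0.5 SD (86.0 less 69.5 to 62.1). The required sample is about 1.6 to 1.8 times as large (100/64 to 114/64). With all patients pooled, the loss at 0.5 SD is 1-2 points and matters only for smaller effects.

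A reader might infer three stronger things that the documents do not support:
- **Inflated false positives.** The test holds its level between independent arms and is conservative on the before/after reading.
- **A fixed 16-24 point loss.** That figure rests on assumed allocation, effect, cuts and normality.
- **No control arm.** The abstract states a randomized controlled trial. Research Steps describes only trained subjects, but the process diagram is not shown, so its absence cannot be concluded.

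**What to change.** Replace the chi-squared sentence with:

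> Within each disease group, the week-2 numeric symptom score is compared between arms by ANCOVA adjusted for the baseline score (rank-based ANCOVA if clearly non-normal), reported as an adjusted difference with 95% CI; the share improved is secondary.

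Name one symptom score per disease group, so that the three hypotheses give three main comparisons and not one for every questionnaire. Define the cut for the share improved in advance.

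Do not use the IBS diagnostic criteria as a change outcome: windows of three and six months cannot register change over two weeks. Use a numeric scale already collected, such as the GSRS, for that group.

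If there is no concurrent control arm, report within-person change with a paired analysis and do not call it efficacy. A more powerful paired test would not separate a treatment effect from placebo response or regression to the mean.

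The cost is protocol wording and slightly more analysis work, with the same data, visits and participants. The downside is a less simple summary than a percentage.

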### ANS Protocol (It takes about 15 minutes)

The ANS Protocol is a standardized and validated method used to assess the autonomic nervous system's (ANS) responses to baseline conditions and stress stimuli. It consists of three stages: a resting phase (5 minutes), a mental arithmetic test under stress conditions (3 minutes), and a recovery period (5 minutes) during which heart rate variability (HRV) is measured. The mental arithmetic test involves subjects performing continuous subtraction of 7 from a randomly generated four-digit number using mental calculation only. If an error occurs, the process is restarted, and the entire procedure lasts for 3 minutes.

ANS Detection Steps :

- 1. Confirm that the status indicator light is in a measurable state (LED color: green), and then attach the electrode patches. •
- 2. R (Red dot): Please paste on the inner side of the right wrist.
- 3. L (Yellow dot): Please paste on the inner side of the left wrist.
- 4. F (Green Marking): Please paste on the inside of the left wrist.
- 5. Press the measurement button on the device to initiate the measurement.
- 6. Before the formal commencement of measurements, the device will conduct a preliminary signal quality check. Participants are advised to remain still and refrain from engaging in conversation during this process.
- 7. The measurement officially begins at 7: Please instruct the subjects to remain still and refrain from talking, waiting quietly for 3 to 5 minutes until the measurement is completed. •
- 8. Measurement Completed: Display Measurement Results.

The HRV indicators for assessing the ANS are as follows : 

- 1. Time Domain Indicators
  - The square root of the mean of the sum of the squares of the Successive differences (RMSSD) : Assessing Parasympathetic Nervous System Activity

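### Efficacy rests on six unranked questionnaires at an unadjusted P<0.05, with none tied to the disease-specific symptom hypotheses, so false efficacy claims are likelier than the threshold suggests

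*Protocol*

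**What the plan says.** The protocol's Statistical Analysis section (part H) presents treatment effectiveness as a percentage improvement, before to after treatment, on six instruments: "sleep habit questionnaire, depression questionnaire, anxiety questionnaire, stress questionnaire, digestive symptom questionnaire, and irritable bowel syndrome questionnaire". It then gives the test, "The efficacy of diaphragmatic breathing was assessed using a Chi-squared test to compare percentages", and the threshold, "A P-value less than 0.05 was considered statistically significant". The section does not rank the six, adjust the threshold, or say how many must be significant.

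Hypothesis 2 is a single overall claim, "Diaphragmatic breathing can improve symptoms in patients with DGBI", followed by three separate ones for LPR (2-1), functional dyspepsia (FD, 2-2) and irritable bowel syndrome (IBS, 2-3). None names the outcome on which it will be judged.

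Two other sections bear on this. The LPR inclusion criteria use an RSI total above 13 to define that cohort. The Questionnaire Evaluation Tool section lists twelve instruments, five disease-related and seven on physical and mental stress. The six labels in the Statistical Analysis section are not matched to them by name.

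**The concern.** A 5% threshold gives a 5% error rate for one test. The efficacy claim here can draw on six tests, or on 18 if each disease cohort is analysed separately, and nothing says which of them decides.

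The list also fits the hypotheses poorly. Hypotheses 2-1 to 2-3 concern the symptoms of three diseases, yet four of the six scales measure sleep, depression, anxiety and stress. For LPR no disease-specific measure is evident in the list, because a digestive symptom questionnaire is not obviously the RSI. A small P-value on sleep or stress could therefore be reported as efficacy in a disease whose own symptoms did not change, and the plan contains nothing to prevent it.

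**Working it through.** **Inputs from the protocol.** Threshold 0.05 per test, six questionnaires, and a Chi-squared test treated as two-sided because it has no direction (Statistical Analysis). Three disease hypotheses (Hypothesis 2). Three separate disease cohorts of 150 each (Participant). The plan offers no derived error rate to reproduce; 0.05 is a set threshold, and for one test it gives 1 − 0.95 = 0.05.

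**Assumptions.**
- Each single test is valid at 5%.
- Any one significant scale may be used to support the claim.
- The correlation between the six scales, which the protocol does not give, is varied from 0 to 0.9.
- Cohorts are independent, being different people.

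**Independent tests.** The chance of at least one false positive among k tests is 1 − 0.95^k.
- Six tests (one cohort, or all cohorts pooled): 1 − 0.95^6 = 0.265.
- Eighteen tests (6 × 3 cohorts): 1 − 0.95^18 = 0.603.

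A false claim of benefit needs a result in the favourable direction, which has probability 0.025 per test.
- Six tests: 1 − 0.975^6 = 0.141.
- Eighteen tests: 1 − 0.975^18 = 0.366.

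**Correlated scales.** Six equally correlated standard normal statistics were simulated (400,000 replicates), with each test rejecting beyond ±1.96. If p is the result for one cohort, three independent cohorts give 1 − (1 − p)^3; for example, at correlation 0.9, 1 − (1 − 0.108)^3 = 0.290. The 18-test columns use unrounded p.

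| Correlation | 6 tests, any direction | 18 tests, any direction | 6 tests, benefit only | 18 tests, benefit only |
|---|---|---|---|---|
| 0 | 26.5% | 60.3% | 14.1% | 36.6% |
| 0.3 | 24.1% | 56.3% | 12.2% | 32.3% |
| 0.5 | 20.7% | 50.1% | 10.3% | 27.8% |
| 0.7 | 16.4% | 41.5% | 8.2% | 22.5% |
| 0.9 | 10.8% | 29.0% | 5.4% | 15.4% |

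For a single test the comparators are 5% in any direction and 2.5% for benefit.

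**With one primary outcome per disease.**
- Each tested at 0.05: 5% per disease and 1 − 0.95^3 = 14.3% over the three.
- Holm at an overall 0.05, when no effect exists anywhere: the chance of any rejection is set by the first step, 0.05/3 = 0.0167, so 1 − (1 − 0.0167)^3 = 4.9%.

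**The case against.** The strongest reply is that this is an omission rather than an error. The section gives a conventional threshold and never says that one positive questionnaire is enough. A multiplicity method is often left to the SAP, which is not at hand. The front part of the protocol is also missing from the text, so the absence of a primary outcome can be asserted only for what is shown. All of this stands as a limit on the wording. It does not remove the point: the protocol itself fixes the list, the test and the threshold, and choosing the outcome that decides each hypothesis is a protocol matter.

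Separate testing by cohort is inferred from Hypotheses 2-1 to 2-3, since the section does not say whether cohorts are pooled. If they are pooled, the family has six tests. If they are separate, control within each disease is a defensible convention. That is why both counts are given. It is also fair that, for benefit only and at correlation 0.9, six tests reach just 5.4%; that is still about twice the 2.5% for one test.

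Sleep and stress are legitimate interests, as the abstract and the expected tasks cover psychological as well as bodily symptoms. They remain poor evidence for hypotheses about disease symptoms.

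A reader might infer larger numbers, and the document does not support them.
- Counting the week-1 and week-2 visits gives 36 tests and 1 − 0.95^36 = 84%. But the plan compares before with after treatment, Research Steps calls the week-2 assessment final, and repeated scores in the same people are not independent.
- Four HRV indices, three stages and three post-baseline recordings give 36 contrasts per cohort. But the efficacy analysis lists only questionnaires and specifies no HRV test.

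**Conclusion.** The point holds in a limited form. The stated threshold does not control the error of the efficacy claim, and no outcome in the text at hand is tied to Hypotheses 2-1 to 2-3. If any one significant scale may carry the claim, the chance of at least one false positive is about 11–26% for six tests and 29–60% for 18. For false claims of benefit it is about 5–14% and 15–37%, against 2.5% for a single test. The upper ends assume independent scales and the lower ends a correlation of 0.9; both are assumptions. All figures take each Chi-squared test as valid at 5%, although the section does not say which percentages are compared.

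It would go too far to say that the protocol declares efficacy on any single positive scale. It sets no rule either way, and that gap is the defect.

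**What to change.** In the Statistical Analysis section, before any results are seen, name one disease-specific symptom score at the final week-2 visit as the primary outcome for each disease, from scales already collected. For example:
- **LPR:** the RSI.
- **FD:** the FD symptom score, once its range is reconciled. Items scored 0–6 cannot total 52, since eight items give 48 and nine give 54.
- **IBS:** the Gastrointestinal Symptom Rating Scale, because the IBS entry in the Questionnaire Evaluation Tool section is a diagnostic criterion with no score.

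Test these three with Holm at an overall two-sided 0.05. Report the other questionnaires, the week-1 visit and the HRV indices as secondary or mechanistic, with confidence intervals and no efficacy claim. The HRV hypotheses need not share the symptom family.

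The choice of scales is the sponsor's; fixing them in advance is what restores the error rate. No new visit, instrument or participant is needed. The price is a first Holm step of 0.05/3 = 0.0167, and secondary scales can no longer carry the claim. The loss of power cannot be calculated, because the Participant section gives 600 participants without an effect size or power.
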